3 HYPOTHESES, OBJECTIVES, AND ENDPOINTS

Hypotheses are aligned with objectives in the Objectives and Endpoints table.

In male and female, programmed cell death 1 protein (PD-1) naïve, participants ≥ 18 years of age with either

- rrcHL who have failed to respond or relapsed after ≥ 1 line of multiagent therapy (can include brentuximab vedotin), or who have failed to achieve a complete response (CR) or relapsed after auto-stem cell transplantation (SCT), or are ineligible for auto-SCT,

OR

- rrPMBCL who have failed to respond or relapsed after ≥ 2 lines of therapy (at least 1 of the prior lines of therapy must contain a rituximab-based regimen), or who have failed to achieve a CR or relapsed after auto-SCT, or are ineligible for auto-SCT:

Primary Objective	Primary Endpoint
To evaluate objective response rate (ORR), by cohort, rrcHL and rrPMBCL, as assessed by the investigator according to Lugano classification criteria [Cheson, B. D., et al 2014] in individuals treated with pembrolizumab Q6W.	Participants with complete response (CR) or partial response (PR).
Secondary Objectives	Secondary Endpoints
To evaluate objective response rate (ORR), by cohort, rrcHL and rrPMBCL, as assessed by blinded independent central review (BICR) according to Lugano classification criteria [Cheson, B. D., et al 2014] in individuals treated with pembrolizumab Q6W.	Participants with complete response CR or PR.
To evaluate duration of response (DOR), by cohort, rrcHL and rrPMBCL, as assessed by the investigator according to Lugano classification criteria [Cheson, B. D., et al 2014] in individuals treated with pembrolizumab Q6W.	The time from first documented evidence of CR or PR until disease progression or death due to any cause, whichever occurs first.

To evaluate duration of response (DOR), by cohort, rrcHL and rrPMBCL, as assessed by BICR according to Lugano classification criteria [Cheson, B. D., et al 2014] in individuals treated with pembrolizumab Q6W.	The time from first documented evidence of CR or PR until disease progression or death due to any cause, whichever occurs first.
To evaluate the pharmacokinetic (PK) profile, immunogenicity of pembrolizumab 400 mg Q6W.	-PK parameters of pembrolizumab including AUC, C _{max} and C _{min} . -Antidrug antibody levels.
To evaluate the safety and tolerability of pembrolizumab Q6W.	-Adverse Events (AEs). -Discontinuations due to AEs.
Tertiary/Exploratory Objectives	Tertiary/Exploratory Endpoints
CCI	[REDACTED]
[REDACTED]	[REDACTED]

4 STUDY DESIGN

4.1 Overall Design

This is a Phase 2, nonrandomized, multisite, open-label study of the efficacy and safety of IV pembrolizumab 400 mg Q6W in adult participants with rrCHL or rrPMBCL. Participants should be PD-1 naïve.

Participants with rrCHL (Cohort 1) must have failed to respond or relapsed after at least 1 line of multiagent therapy (chemotherapy with or without brentuximab vedotin), or have failed to achieve CR or relapsed after an auto-SCT, or are ineligible for auto-SCT.

Participants with rrPMBCL (Cohort 2) must have failed to respond or relapsed after ≥ 2 lines of prior therapy, or failed to achieve a CR or relapsed after auto-SCT or are ineligible for auto-SCT. At least 1 of the prior lines of therapy must contain a rituximab-based regimen. Participants with rrPMBCL must not require urgent cytoreductive therapy.

The study design is summarized in [Figure 1](#). The planned objectives and endpoints are detailed in Section 3.

After Screening, approximately 60 participants will receive pembrolizumab 400 mg fixed dose administered Q6W for up to 18 cycles (approximately 2 years) until documented disease progression per investigator assessment according to Lugano classification or the participant meets 1 of the discontinuation criteria (Section 7.1).

Disease will be assessed every 12 weeks using the Lugano response criteria [Cheson, B. D., et al 2014] per investigator assessment.

Participants who discontinue treatment for reasons other than disease progression will have posttreatment follow-up for disease status until disease progression, initiating a non-study cancer treatment, withdrawing consent, death, or becoming lost to follow-up. All participants will be followed for OS until death, withdrawal of consent, the end of the study, or becoming lost to follow-up, whichever comes first.

AEs will be monitored throughout the study and graded in severity according to the guidelines outlined in the NCI CTCAE 5.0. After the end-of-treatment, each participant will be followed for AE monitoring (see Section 8.4). Participants who undergo allogeneic SCT within 2 years after their last dose of study treatment will be followed for ECIs for up to 18 months post-transplant. This additional follow-up for participants undergoing an allogeneic SCT within 2 years after their last treatment is necessary to provide data for a post-marketing requirement from the FDA.

Specific procedures to be performed during the study, including prescribed times and associated visit windows, are outlined in Section 1.3 of the SoA. Details of each procedure are provided in Section 8.

4.2 Scientific Rationale for Study Design

This is a Phase 2, nonrandomized, multisite, open-label study of the efficacy and safety of IV pembrolizumab 400 mg Q6W in adult, PD-1 naïve, participants with rrcHL or rrPMBCL.

The rationale for selected dose and dosing schedule are summarized in Section 2.1 and Section 4.3. The study includes 2 cohorts (rrcHL or rrPMBCL); enrollment into each cohort will not be controlled as the number of rrPMBCL participants could vary since this is a rare form of DLBCL.

The study is open-label as pembrolizumab is already approved for use in the rrcHL and rrPMBCL, making blinding unnecessary.

[figure not shown]
The results of this study will contribute to an understanding of the PK characteristics of pembrolizumab administered in a Q6W dosing regimen in rrcHL and rrPMBCL.

4.2.1 Rationale for Endpoints

4.2.1.1 Efficacy Endpoints

The primary endpoint for this study will be the achievement of objective response, meaning a best overall response of PR or CR, defined according to the Lugano classification [Cheson, B. D., et al 2014], as assessed by the investigator. Response assessment per Lugano includes anatomic imaging (CT), metabolic imaging (FDG-PET), and clinical information. The proportion of participants in a treatment group who achieve an objective response is called the ORR. ORR is an acceptable measure of clinical benefit for a late-stage study that demonstrates superiority of a new antineoplastic therapy, especially if the magnitude of the effect is large and the therapy has an acceptable benefit/risk profile. The Lugano classification, published in 2014, is the revised response criteria for assessing ORR in HL and NHL and recommended by the current NCCN guidelines for B-cell lymphoma [National Comprehensive Cancer Network 2019]. All images and clinical data will be assessed by the investigator.

CCI

[figure not shown]

4.2.1.2 Safety Endpoints

A secondary objective of this study is to characterize the safety and tolerability of 400 mg pembrolizumab when administered IV Q6W.

Safety parameters frequently used for evaluating investigational-systemic anticancer treatments are included as safety endpoints including, but not limited to, the incidence of, causality, and outcome of AEs/SAEs, and changes in vital signs and laboratory values. AEs will be assessed as defined by CTCAE, Version 5.0.

CCI

4.2.1.3 Pharmacokinetic Endpoints

An objective of this study is to characterize the PK profile of pembrolizumab after administration as an IV infusion Q6W. PK data will be analyzed after all participants complete Cycle 5. PK parameters will include AUC, Cmax, and Cmin. Results of PK analysis will be provided in a separate report added to the CSR as an appendix.

4.2.1.4 Antidrug Antibodies (ADA)

[figure not shown]
[figure not shown]
Formation of ADAs can potentially confound drug exposures at therapeutic doses and prime for subsequent infusion-related toxicity. ADA response to pembrolizumab at the beginning of each of the first 5 cycles will be determined. Any impact of presence of ADAs on exposure of pembrolizumab will be explored. Results of ADA analysis will be provided in a separate report added to the CSR as an appendix.

4.2.1.5 Pharmacodynamic Endpoints

[figure not shown]
There are no pharmacodynamic endpoints in this study.

4.2.1.6

CCI

CCI

CCI

4.2.1.7 CCI

4.2.2 Rationale for the Use of Comparator/Placebo

Not applicable.

4.3 Justification for Dose

The current approved dosing regimen of pembrolizumab for an IV administration are 200 mg Q3W or 400 mg Q6W for adults.

A 400 mg Q6W dosing regimen of pembrolizumab is expected to have a similar benefit/risk profile as 200 mg Q3W, in all treatment settings in which 200 mg Q3W pembrolizumab is currently appropriate [Lala, M., et al 2020]. Specifically, the dosing regimen of 400 mg Q6W for pembrolizumab is considered adequate based on modeling and simulation analyses, given the following rationale:

- PK simulations demonstrating that in terms of pembrolizumab exposures:
 - Average concentration over the dosing interval C_{avg} (or AUC) at 400 mg Q6W is similar to the approved 200 mg Q3W dose, thus bridging efficacy between dosing regimens.
 - Trough concentrations (C_{min}) at 400 mg Q6W are generally within the range of those achieved with 2 mg/kg or 200 mg Q3W in the majority (>99%) of participants.
 - Peak concentrations (C_{max}) at 400 mg Q6W are well below the C_{max} for the highest clinically tested dose of 10 mg/kg every 2 weeks, supporting that the safety profile for 400 mg Q6W should be comparable to the established safety profile of pembrolizumab.

- Exposure-response for pembrolizumab has been shown to be flat across indications, and OS predictions in melanoma and NSCLC show that efficacy at 400 mg Q6W is expected to be similar to 200 mg or 2 mg/kg Q3W, given the similar exposures; thus, 400 mg Q6W is expected to be efficacious across indications.

4.3.1 Starting Dose for This Study

The study will use pembrolizumab at a fixed dose of 400 mg Q6W.

4.3.2 Maximum Dose Exposure for This Study

All participants may receive up to 18 infusions of pembrolizumab (approximately 2 years) or until confirmed PD, whichever comes first.

4.4 Beginning and End-of-Study Definition

The overall study begins when the first participant (or their legally acceptable representative) provides documented informed consent. The overall study ends when the last participant completes the last study-related contact, withdraws consent, or is lost to follow-up (Section 7.3). For purposes of analysis and reporting, the overall study ends when the Sponsor receives the last laboratory test result or at the time of final contact with the last participant, whichever comes last.

If the study includes countries in the European Economic Area (EEA), the local start of the study in the EEA is defined as First Site Ready (FSR) in any Member State.

4.4.1 Clinical Criteria for Early Study Termination

The clinical study may be terminated early if the extent (incidence and/or severity) of emerging effects/clinical endpoints is such that the risk/benefit ratio to the study population as a whole is unacceptable. In addition, further recruitment in the study or at (a) particular study site(s) may be stopped due to insufficient compliance with the protocol, GCP, and/or other applicable regulatory requirements, procedure-related problems or the number of discontinuations for administrative reasons is too high.

5 STUDY POPULATION

As stated in the Code of Conduct for Clinical Trials (Appendix 1.1), this study includes participants of varying age (as applicable), race, ethnicity, and sex (as applicable). The collection and use of these demographic data will follow all local laws and participant confidentiality guidelines while supporting the study of the disease, its related factors, and the IMP under investigation.

Prospective approval of protocol deviations to recruitment and enrollment criteria, also known as protocol waivers or exemptions, is not permitted.

5.1 Inclusion Criteria

An individual is eligible for inclusion in the study if the individual meets all of the following criteria:

Type of Participant and Disease Characteristics

1. Male/female participants who are at least 18 years of age on the day of documented informed consent.
2. Have a histologically confirmed diagnosis of cHL or PMBCL, according to the WHO classification of neoplasms of the hematopoietic and lymphoid tissues [Swerdlow, S. H., et al 2008].
3. Have radiographically measurable cHL or PMBCL disease as per Lugano classification with at least 1 nodal lesion (which has not been previously radiated) that is >15 mm in long axis, regardless of the length of the short axis, and/or extranodal lesion of >10 mm in long and short axis.

PMBCL-Specific Disease Characteristics:

4. Have relapsed^a or refractory^b PMBCL and:
 - Have relapsed after auto-SCT or have failed to achieve a CR or PR within 60 days of auto-SCT. Participants may have received intervening therapy after auto-SCT for relapsed or refractory disease, in which case they must have relapsed after or be refractory to their last treatment.

OR

- For participants who are ineligible for auto-SCT, have received at least ≥ 2 lines of prior therapy and have failed to respond to or relapsed after their last line of treatment. At least 1 of the prior lines of therapy must contain a rituximab-based regimen. For participants who received consolidative local radiotherapy after systemic therapy, local radiotherapy will not be considered as a separate line of treatment.

Note: Participants should not need urgent cytoreductive therapy.

- ^a **Relapsed Disease:** disease progression after achieving an overall response of PR or CR in response to the most recent therapy
- ^b **Refractory Disease:** failure to achieve CR or PR to the most recent therapy.

cHL-Specific Disease Characteristics:

5. Have relapsed^a or refractory^b cHL and:
 - Have relapsed during their last cHL regimen after receiving at least 2 cycles of therapy or within 12 months after completing the last regimen for cHL.

OR

 - Have received at least ≥ 1 line of prior multiagent therapy with/without brentuximab vedotin (excluding radiation) or auto-SCT for cHL and have failed to respond to or relapsed after their last line of treatment (for country-specific requirements see Appendix 7).

*^a **Relapsed Disease:** disease progression after achieving an overall response of PR or CR to the most recent therapy

*^b **Refractory Disease:** failure to achieve CR or PR to the most recent therapy.

Demographics

6. A female participant is eligible to participate if she is not pregnant or breastfeeding, and at least one of the following conditions applies:
 - Is not a WOCBP

OR

 - Is a WOCBP and using a contraceptive method that is highly effective (with a failure rate of <1% per year) or be abstinent from heterosexual intercourse as their preferred and usual lifestyle (abstinent on a long-term and persistent basis), as described in Appendix 5 during the intervention period and for at least 120 days after the last dose of study intervention. The investigator should evaluate the potential for contraceptive method failure (ie, noncompliance, recently initiated) in relationship to the first dose of study intervention.
 - A WOCBP must have a negative highly sensitive pregnancy test (urine or serum, as required by local regulations) within 24 hours for urine or within 72 hours for serum before the first dose of study intervention.
 - If a urine test cannot be confirmed as negative (eg, an ambiguous result), a serum pregnancy test is required. In such cases, the participant must be excluded from participation if the serum pregnancy result is positive.

- Abstains from breastfeeding during the study intervention period and for at least 120 days after study intervention.
- Additional requirements for pregnancy testing during and after study intervention are in Section 8.3.5.
- The investigator is responsible for review of medical history, menstrual history, and recent sexual activity to decrease the risk for inclusion of a woman with an early undetected pregnancy.
- Contraceptive use by women should be consistent with local regulations regarding the methods of contraception for those participating in clinical studies.

Informed Consent

7. The participant (or legally acceptable representative) has provided documented informed consent/assent for the study. The participant may also provide consent/assent for FBR. However, the participant may participate in the study without participating in FBR.

Additional Categories

8. Submit an evaluable core lymph node biopsy for biomarker analysis from an archival (>60 days) or newly obtained core or incisional (within 30 days) biopsy, which was not previously irradiated at Screening (Visit 1).
Note: If no archival tissue is available, 2 new fresh core needle samples are required.
9. Have an ECOG Performance Status of 0 to 1 assessed within 7 days before allocation.
10. Life expectancy >3 months.
11. Have blood oxygen saturation >92%.
12. Have adequate organ function as defined in the following table ([Table 2](#)). Specimens must be collected within 7 days before the start of study intervention.

Table 2 Adequate Organ Function Laboratory Values

System	Laboratory Value
Hematological	
Absolute neutrophil count (ANC)	$\geq 1000/\mu\text{L}$ (unless marrow involvement)
Platelets ^a	$\geq 75\,000/\mu\text{L}$ (unless marrow involvement)
Hemoglobin ^a	$\geq 8.0\text{ g/dL}$ or $\geq 5.6\text{ mmol/L}^a$ (unless marrow involvement)
Renal	
Creatinine	$\leq 1.5 \times \text{ULN}$
OR	
Measured or calculated creatinine clearance (GFR can also be used in place of creatinine or CrCl)	$\geq 30\text{ mL/min}$
Hepatic	
Total bilirubin	$\leq 1.5 \times \text{ULN}$
	OR
	direct bilirubin $\leq \text{ULN}$ for participants with total bilirubin levels $>1.5 \times \text{ULN}$
AST (SGOT) and ALT (SGPT)	$\leq 2.5 \times \text{ULN}$ ($\leq 5 \times \text{ULN}$ for participants with liver metastases)
Coagulation	
International normalized ratio (INR) or prothrombin time (PT)	$\leq 1.5 \times \text{ULN}$ unless participant is receiving anticoagulant therapy as long as PT or PTT is within therapeutic range of intended use of anticoagulants
Activated partial thromboplastin time (aPTT)	$\leq 1.5 \times \text{ULN}$ unless participant is receiving anticoagulant therapy as long as PT or PTT is within therapeutic range of intended use of anticoagulants
ALT (SGPT)=alanine aminotransferase (serum glutamic pyruvic transaminase); AST (SGOT)=aspartate aminotransferase (serum glutamic oxaloacetic transaminase); GFR=glomerular filtration rate; ULN=upper limit of normal.	
^a Criteria must be met without erythropoietin dependency and without packed red blood cell (pRBC) transfusion within last 2 weeks prior to first dose of study intervention.	

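### The haemoglobin limit in Table 2 is printed as 8.0 g/dL or 5.6 mmol/L, but these are not the same concentration: they differ by about 1.0 g/dL

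*Combined protocol and SAP*

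**What the plan says.** Criterion 12 in Section 5.1 reads "Have adequate organ function as defined in the following table" and points to Table 2. The haemoglobin row there, as extracted with its typesetting code, gives the limit as "8.0\text{ g/dL}$ or $\geq 5.6\text{ mmol/L". The row shows two minimum values, one in mass units and one in molar units, joined by a plain 'or' and sharing one exception for marrow involvement.

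Footnote a, attached to this row, says "Criteria must be met without erythropoietin dependency and without packed red blood cell (pRBC) transfusion" within the two weeks before the first dose. It says nothing about units.

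Two other statements make the row binding. Section 5.1 opens with "An individual is eligible for inclusion in the study if the individual meets all of the following criteria". Section 5 says of deviations from the recruitment and enrolment criteria that their prospective approval, "also known as protocol waivers or exemptions, is not permitted".

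**The concern.** The row gives one analyte in two units, so it reads most naturally as a single limit restated for laboratories that report differently. As a restatement it fails, because the molar figure corresponds to a haemoglobin roughly 1 g/dL higher than the mass figure.

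What is at stake depends on how the 'or' is read.

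1. **Each laboratory uses the figure for its own unit.** A candidate without marrow involvement whose haemoglobin lies between 8.0 and about 9.0 g/dL (about 5.0 to 5.6 mmol/L) passes where results come in g/dL and fails where they come in mmol/L. The study is multisite and does not permit waivers, so a site has no sanctioned way round the figure it applies.
2. **Meeting either figure is enough.** Nobody is treated differently by unit. The 5.6 mmol/L figure then never decides anything, because anyone who reaches it is already above 8.0 g/dL, and it misleads a site that applies it alone.

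**Working it through.** **Inputs**
- Printed limits, from Table 2: 8.0 g/dL and 5.6 mmol/L.
- Molar mass M of haemoglobin: not in the documents. Assumed to be the monomer, about 16,114 g/mol, with a range of 16,000 to 16,125 (0.625 to 0.620 mmol/L per g/dL).
- Tetramer variant: assumed 64,000 to 64,500 g/mol.

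**Formulas** (M in g/mmol, that is g/mol divided by 1,000)
- mmol/L = (g/dL × 10) / M
- g/dL = (mmol/L × M) / 10

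**Attempt to reproduce the printed pair**

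| M (g/mmol) | 8.0 g/dL in mmol/L | 5.6 mmol/L in g/dL | Gap, g/dL | Gap, % of 8.0 | Gap, mmol/L |
|---|---|---|---|---|---|
| 16.000 | 80/16.000 = 5.00 | 5.6 × 16.000/10 = 8.96 | 0.96 | 12.0 | 0.60 |
| 16.114 | 80/16.114 = 4.96 | 5.6 × 16.114/10 = 9.02 | 1.02 | 12.8 | 0.64 |
| 16.125 | 80/16.125 = 4.96 | 5.6 × 16.125/10 = 9.03 | 1.03 | 12.9 | 0.64 |

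No value of M in the range turns 8.0 g/dL into 5.6 mmol/L.

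**Could rounding explain it?** Take the rounding most favourable to agreement, with 8.0 standing for 8.05 and 5.6 standing for 5.55:
- M = 16.000: 5.55 × 16.000/10 − 8.05 = 8.88 − 8.05 = 0.83 g/dL
- M = 16.114: 0.89 g/dL
- M = 16.125: 0.90 g/dL

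At least 0.83 g/dL remains.

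**Could a tetramer basis explain it?** 80/64.0 = 1.25 and 80/64.5 = 1.24 mmol/L. That is further from 5.6, not closer.

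**What molar mass does the printed pair imply?** 80/5.6 = 14.286 g/mmol, or about 14,286 g/mol. With rounding, the bounds are 79.5/5.65 = 14.071 and 80.5/5.55 = 14.505. The upper bound still falls short of 16.000.

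**Could the text explain it?** Footnote a covers only erythropoietin and transfusion. No other visible section states a haemoglobin limit that would show which figure was meant.

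**The case against.** The arithmetic is not in dispute, but four points can be made against its importance.

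- **The digit may be misread.** The text was extracted by a program and has errors elsewhere, mostly at redactions or symbols. One changed digit, 5.0 for 5.6 or 9.0 for 8.0, would remove the mismatch. This stands as a reason to check the source first. It does not dispose of the point: the row is complete, the rest of Table 2 reads cleanly, and nothing visible suggests this digit is wrong.
- **Table 2 uses 'or' for true alternatives elsewhere.** Creatinine or clearance, and total or direct bilirubin, are rows where meeting either suffices. Read the same way, the haemoglobin row is met at 8.0 g/dL in any unit. This makes the harmless reading possible but does not settle it, since those rows join different measurements and this one gives a single measurement in two units.
- **No misclassification is shown.** Harm requires the first reading, a laboratory reporting mmol/L, no conversion by the site, a value in the band and no marrow involvement. This stands: the documents do not give the sites' units or the number affected.
- **There is no analytical consequence.** The study estimates ORR without hypothesis tests, and its calculation does not change. This also stands, and it limits the weight of the point.

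**Conclusion.** The concern holds. As printed, the two haemoglobin figures are not equivalent: the gap is 1.02 g/dL (range 0.96 to 1.03), or 12.8% of the g/dL figure (12.0% to 12.9%). This rests on the assumed monomer mass of 16,000 to 16,125 g/mol and on the row being as extracted. Confidence in the arithmetic is high; confidence about how many candidates are affected is low.

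The point is worth fixing because the wrong figure sits in a binding eligibility criterion that cannot be waived. The documents do not show which figure was intended.

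**What to change.** 1. Check the haemoglobin row against the source document. If the mismatch is only an extraction error, nothing more is needed.
2. If it is real, the sponsor should confirm the intended value and recompute the other. 8.0 g/dL pairs with about 5.0 mmol/L; 5.6 mmol/L pairs with about 9.0 g/dL. The choice is the sponsor's.
3. Issue a protocol clarification with the reconciled pair.
4. If screening has begun, review candidates without marrow involvement in the 8.0 to 9.0 g/dL band, according to the value confirmed. If the g/dL figure was intended, look at screen failures at sites that applied the mmol/L figure. If the mmol/L figure was intended, look at participants enrolled under the g/dL figure.

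The cost is one number in Table 2 and, if screening has started, one query of screening haemoglobin values over a band about 1 g/dL wide. The statistical analysis plan needs no change.
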